7.1.2 Randomization (Visit 2, Day 0)

The following procedures will be performed on Day 0 (randomization). Ophthalmic procedures should be performed in the order suggested below:

- Determine study eligibility based on Inclusion/Exclusion criteria.
- BCVA
- Biomicroscopy
- Diurnal IOP
 - Measured using Goldmann applanation tonometer and a two-person reading method.
 - Readings at:
 - 8:00AM (± 30 mins)
 - 10:00AM (± 30 mins)
 - 4:00PM (± 30 mins)
 - Measure twice in each eye; if results differ by >1 mm Hg, a third measurement will be obtained. The mean will be taken if two measurements are used, for 3 measurements record the median.
- Blood pressure & heart rate
- Randomization
- Urine pregnancy test (UPT) for women of childbearing potential

- An adult woman is considered to be of childbearing potential unless she is one year post-menopausal or three months post-surgical sterilization.
- Assess subject ability to instill drops in eye using artificial tears. Subjects should be retrained on the correct way to instill drops if they are not able to do so.
- Update medical and ocular history, as needed
- Update concomitant medications, as needed

7.1.3 Visit 3 (Day 1)

The following procedures will be performed at Visit 3 (Day 1). Ophthalmic procedures should be performed in the order suggested below:

- BCVA
- Biomicroscopy
- IOP
 - Measured using Goldmann applanation tonometer and a two-person reading method.
 - Reading at:
 - 8:00AM (± 30 mins)
 - Measure twice in each eye; if results differ by >1 mm Hg, a third measurement will be obtained. The mean will be taken if two measurements are used, for 3 measurements record the median.
- Administer first dose of study drug in clinic after IOP is taken.
- Dispense study drug
- Instruct subject to dose daily in the morning (suggested timing between 7:00AM and 9:00AM).
- Blood pressure & heart rate
- Update concomitant medications, as needed
- Adverse event assessment

7.1.4 Visit 4 (Day 7 + 2 days)

Visit 4 needs should be scheduled 5 days after Visit 3 in order to ensure at least 7 days of q.d. dosing in the morning.

The following procedures will be performed at Visit 4 (Day 7). Ophthalmic procedures should be performed in the order suggested below:

- BCVA
- Biomicroscopy
- Diurnal IOP

- Measured using Goldmann applanation tonometer and a two-person reading method.
- Readings at:
 - 8:00AM (± 30 mins)
 - 10:00AM (± 30 mins)
 - 4:00PM (± 30 mins)
- Measure twice in each eye; if results differ by >1 mm Hg, a third measurement will be obtained. The mean will be taken if two measurements are used, for 3 measurements record the median.
- Administer last q.d. morning dose in clinic after 8:00AM IOP is taken.
- Collect used study drug and dispense a new bottle.
- Instruct subject to start dosing daily the day after the visit in the evening (suggested timing between 7:00PM and 9:00PM).
- Blood pressure & heart rate
- Update concomitant medications, as needed
- Adverse event assessment

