3.1 Overall Design of the Study

This is a prospective, parallel-comparison, multi-center, double-masked, randomized, vehicle-controlled dose-response study assessing the safety and ocular hypotensive efficacy of VVN539 in subjects with POAG or OHT. Approximately 60 subjects will be randomized into one of two active treatment arms or a control arm (20 subjects per cohort):

- Arm 1: 0.02% VVN539 ophthalmic solution
- Arm 2: 0.04% VVN539 ophthalmic solution
- Arm 3: VVN539 ophthalmic solution vehicle

Treatment assignments will be masked to VivaVision, study subjects, Investigators, and site staff.

The study involves 6 clinic visits, including screening, baseline, and treatment visits. The study is open to subjects with OHT and POAG who are either treatment-naïve or are already on ocular hypotensive medication. Subjects on ocular hypotensive who meet screening inclusion and do not meet screening exclusion criteria at Visit 1 will discontinue their prior ocular hypotensive medication for up to 35 days before returning to the site for Visit 2 (baseline). Treatment naïve subjects can return for the baseline visit as early as the day after Visit 1. Subjects meeting all baseline inclusion criteria and none of the baseline exclusion criteria will be randomized into one of the study arms and will return to the study site the next day for the first treatment. Three different dosing regimens (once a day [q.d.] in the morning, q.d. in the evening and twice a day [b.i.d.]) will be tested for 7-9 days, each.

Figure 1: Study Treatment

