5.1.2 Dosage and Administration

Eligible subjects will be randomized in a 1:1:1 ratio to receive either 0.02% or 0.04% VVN539 or vehicle control. The IP will be administered as 1 drop either q.d. or b.i.d in the inferior conjunctival fornix in each eye.

The first dose of VVN539 will be administered in clinic after the 8:00AM IOP has been measured at Visit 3. The subjects will then receive the bottle of IP and will self-administer the IP in the morning (suggested timing between 7:00AM and 9:00AM) each day for 5 days. The study site should call the subject the day prior to Visit 4 to remind them to NOT dose in the morning at home on the day of the visit. The last day of q.d. morning dosing will be Visit 4 when subjects will be dosing in clinic after the 8:00AM IOP has been measured.

Starting the day after Visit 4, subjects will self-administer the IP in the evening (suggested timing between 7:00PM and 9:00PM) each day for 6 days. The last q.d. evening dose will be administered in the evening Visit 5 after the last IOP has been measured.

Starting the day after Visit 5, subjects will self-administer the IP b.i.d (suggested timing between 7:00AM and 9:00AM for the morning dose and between 7:00PM and 9:00PM for the evening dose) each day for 6 days. The study site should call the subject the day prior to Visit 6 to remind them to NOT dose in the morning at home on the day of the visit. The last morning dose will be administered in clinic after the 8:00AM IOP dose has been measured. Subjects will return the IP at Visit 6 and will resume their standard of care treatment.

Subjects should be instructed to administer missed doses as soon as possible, as long as it is not administered within 12 hours of the next scheduled dosing during the q.d. dosing periods or not within 4 hours of the next scheduled dosing during the b.i.d dosing period. Missed doses will be recorded as deviations in the electronic case report form (eCRF).

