5.2.2 Product Packaging and Labeling

Each randomization kit contains one dropper bottle of IP sufficient for 14-18 days of q.d. and 7-9 days of b.i.d. dosing. Double masked labels will minimally contain the following information:

- Protocol number
- Sponsor's name
- Kit number
- Instructions for use
- Storage temperature
- Required statement(s) per regulatory agency

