7.1.5 Visit 5 (Day 14 + 2 days)

Visit 5 needs should be scheduled 6 days after Visit 4 in order to ensure at least 7 days of q.d. dosing in the PM. The following procedures will be performed at Visit 5 (Day 14). Ophthalmic procedures should be performed in the order suggested below:

- BCVA
- Biomicroscopy
- Diurnal IOP
 - Measured using Goldmann applanation tonometer and a two-person reading method.
 - Readings at:
 - 8:00AM (± 30 mins)
 - 10:00AM (± 30 mins)
 - 4:00PM (± 30 mins)
 - Measure twice in each eye; if results differ by >1 mm Hg, a third measurement will be obtained. The mean will be taken if two measurements are used, for 3 measurements record the median.
- Collect used study drug and dispense a new bottle.
- Instruct subject to instill the last daily evening dose in the evening after the visit (suggested timing between 7:00PM and 9:00PM).

- Instruct subject to start dosing twice daily the day after the visit in the morning (suggested timing between 7:00AM and 9:00AM for the morning dose and between 7:00PM and 9:00PM for the evening dose).
- Blood pressure & heart rate
- Update concomitant medications, as needed
- Adverse event assessment

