7.1.6 End of Study (Visit 6, Day 21 + 2 days)

Visit 6 needs should be scheduled 6 days after Visit 5 in order to ensure at least 6 days of b.i.d. dosing.

The following procedures will be performed at the End of Study visit (Visit 6) on Day 21. Ophthalmic procedures should be performed in the order suggested below:

- BCVA
- Biomicroscopy
- Diurnal IOP
 - Measured using Goldmann applanation tonometer and a two-person reading method.
 - Readings at:
 - 8:00AM (± 30 mins)
 - 10:00AM (± 30 mins)
 - 4:00PM (± 30 mins)
 - Measure twice in each eye; if results differ by >1 mm Hg, a third measurement will be obtained. The mean will be taken if two measurements are used, for 3 measurements record the median.
- Administer last dose of b.i.d. study drug in clinic after 8:00AM IOP is taken.
- Pachymetry
- Dilated ophthalmoscopy
 - After last IOP measurement is taken.
- Blood pressure & heart rate
- Blood chemistry, hematology
- UPT for women of childbearing potential
 - An adult woman is considered to be of childbearing potential unless she is one year post-menopausal or three months post-surgical sterilization.
- Collect used study drug.
- Update concomitant medications, as needed
- Adverse event assessment

- If a non-serious AE is unresolved at the time of the subject's final study visit, an effort will be made to follow up until the AE is resolved or stabilized, the subject is lost to follow-up, or there is some other resolution of the event.
- The Investigator should make every attempt to follow all SAEs to resolution.

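### The visit intervals in Protocol 7.1.4 to 7.1.6 (5, 6 and 6 days) are each one day too short for the protocol's own windows and dosing counts

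*Protocol*

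**What the plan says.** The three treatment visits each carry an interval and a purpose:

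- Protocol 7.1.4: Visit 4 is to be "scheduled 5 days after Visit 3 in order to ensure at least 7 days of q.d. dosing in the morning".
- Protocol 7.1.5: Visit 5 is to be "scheduled 6 days after Visit 4 in order to ensure at least 7 days of q.d. dosing in the PM".
- Protocol 7.1.6: Visit 6 is to be "scheduled 6 days after Visit 5 in order to ensure at least 6 days of b.i.d. dosing".

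The headings of those sections and Appendix 1 put the visits at Days 7, 14 and 21, each with a plus-2-day window and no minus side. Visit 3, with the first dose in clinic, is Day 1 and has no window.

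On regimen length, 3.1 says the three regimens "will be tested for 7-9 days, each", 3.3 plans 7 days of each, and 5.2.2 describes a kit "sufficient for 14-18 days of q.d. and 7-9 days of b.i.d. dosing". Section 5.1.2 gives the dosing pattern:

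- Morning: a clinic dose at Visit 3, 5 home days, and a clinic dose at Visit 4.
- Evening: 6 evenings starting the day after Visit 4, then a last dose on the evening of Visit 5.
- Twice daily: 6 home days starting the day after Visit 5, then a morning clinic dose at Visit 6.

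SAP 9.7.1.4 counts exposure from visit dates: Visit 4 − Visit 3 + 1 for morning, Visit 5 − Visit 4 for evening, and Visit 6 − Visit 5 for twice daily.

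**The concern.** The printed intervals do not lead to the printed visit days, and two of the three do not deliver the dosing minimum named in the same sentence. The figures 5, 6 and 6 are the home-dosing days of 5.1.2, that is, the days lying between visits. They have been written as the distance from one visit to the next, which is one day longer.

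These are operative scheduling instructions for the only visits that supply primary-endpoint data, and each visit stands for one regimen. Because Visit 3 is fixed, a site can never satisfy both the Visit 4 interval and the Visit 4 window. For Visits 5 and 6 the same conflict arises whenever the previous visit fell on its nominal day. Protocol 10.1.8 treats any noncompliance as a deviation, and significant deviations bear on Per Protocol membership. The SAP analyses by nominal CRF visit (9.7.1, Visit Windows), so a Day 6 visit would still be summarised as Visit 4.

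**Working it through.** **Inputs.** Visit 3 = Day 1 (7.1.3, Appendix 1). Windows: Visit 4 Days 7–9, Visit 5 Days 14–16, Visit 6 Days 21–23 (headings of 7.1.4–7.1.6, Appendix 1). Stated intervals: 5, 6, 6 days. Dosing counts: 5.1.2 and SAP 9.7.1.4.

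**Step 1: visit days.** Visit day = previous visit day + interval, taking the previous visit on its nominal day.

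| Visit | As printed | With 6/7/7 | Window |
|---|---|---|---|
| 4 | 1 + 5 = 6 | 1 + 6 = 7 | 7–9 |
| 5 | 7 + 6 = 13 | 7 + 7 = 14 | 14–16 |
| 6 | 14 + 6 = 20 | 14 + 7 = 21 | 21–23 |

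Each printed interval lands one day before its window. If a site followed all three in sequence, the visits would fall on Days 6, 12 and 18, which are 1, 2 and 3 days early. A late previous visit brings the date back into the window: Visit 4 on Day 8 or 9 gives Visit 5 on Day 14 or 15, and Visit 5 on Day 15 or 16 gives Visit 6 on Day 21 or 22. The regimen is still one dosing day short, because the interval is still 6 days.

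**Step 2: dosing days (SAP formulas).**

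| Regimen | As printed | With 6/7/7 | Promised in 7.1.4–7.1.6 |
|---|---|---|---|
| Morning | 6 − 1 + 1 = 6 | 7 − 1 + 1 = 7 | at least 7 |
| Evening | 13 − 7 = 6 | 14 − 7 = 7 | at least 7 |
| Twice daily | 20 − 14 = 6 | 21 − 14 = 7 | at least 6 |
| Full twice-daily days (gap − 1) | 6 − 1 = 5 | 7 − 1 = 6 | – |

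The 6/7/7 column reproduces 5.1.2: morning 1 + 5 + 1 = 7, evening 6 + 1 = 7, twice daily 6 full days plus the clinic dose.

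**Step 3: doses received before the IOP reading.**

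- Visit 4, 8AM: Days 1–5 = 5 as printed; Days 1–6 = 6 corrected.
- Visit 5: evenings of Days 8–12 = 5 as printed; Days 8–13 = 6 corrected.
- Visit 6, 8AM: Days 15–19, 5 × 2 = 10 as printed; Days 15–20, 6 × 2 = 12 corrected.

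**Step 4: would the windows alone be enough?** There are 3 × 3 × 3 = 27 in-window combinations of Visits 4, 5 and 6.

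- Windows only (27): 7–9 morning days, 5–9 evening doses, 4–8 full twice-daily days. The low ends are Visits 4 and 5 on Days 9 and 14 (14 − 9 = 5) and Visits 5 and 6 on Days 16 and 21 (21 − 16 − 1 = 4).
- Printed 5/6/6 read as minimums within the windows: 21 combinations, with as few as 6 evening doses and 5 full twice-daily days.
- At least 6/7/7 within the windows: Visit 4 on Day 7 leaves 3 + 2 + 1 = 6 combinations, on Day 8 leaves 2 + 1 = 3, and on Day 9 leaves 1, so 10 in all. These give 7–9 morning days, 7–9 evening doses, and 7–9 twice-daily days by the SAP formula (6–8 full days plus the clinic dose).

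**The case against.** The best reply is that this is a wording slip, corrected in the same place. Each sentence sits under a heading with the right day, and Appendix 1, 3.3, 5.1.2 and the synopsis all agree with the headings. Read as days between visits, 5/6/6 is consistent with everything else. That stands as an account of the cause and of the intent. It does not change what the sentences instruct: an interval counted from a visit is ordinarily that visit's date plus the interval.

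The twice-daily leg is weaker than the other two. Section 7.1.6 promises only 6 days, and a 6-day gap meets that if the clinic-dose day is counted, as the SAP does. That also stands. The gap nevertheless falls short of 3.1, 3.3 and 5.1.2 and, from a nominal Visit 5, of its window. The Days 6/12/18 sequence is a worst case, since it requires a site to overlook the windows at every visit.

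No effect on the analysis is shown. All arms follow the same schedule, the documents give no IOP effect for one dose fewer, and exposure is reported from actual dates, so a shortfall would be visible, though only afterwards. These points limit the severity.

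Finally, short regimens after a late visit come from the fixed windows, not from the slip, and hard minimums reduce flexibility. Both are true. The minimums are nevertheless what the 7-to-9-day range in 3.1 already implies.

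**Conclusion.** The intervals in 7.1.4–7.1.6 are wrong as written and should be corrected. From nominal previous visits each is one day short: Days 6, 13 and 20 against windows opening on Days 7, 14 and 21. Morning and evening dosing come to 6 against at least 7. Twice-daily dosing comes to 6 days by the SAP count (5 full) against 7 in 3.3.

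The Visit 4 conflict is unconditional, because Visit 3 is fixed. The window conflict for Visits 5 and 6 assumes the previous visit was on its nominal day. The dosing shortfall follows from the interval alone. The consequence lies in site scheduling, deviations and regimen length; no bias between arms follows, and the size of any IOP effect cannot be stated from the documents.

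**What to change.** Replace the intervals in Protocol 7.1.4–7.1.6 as follows, each within its existing Day 7, 14 or 21 (+2) window:

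- Visit 4: at least 6 days after Visit 3.
- Visit 5: at least 7 days after Visit 4.
- Visit 6: at least 7 days after Visit 5.

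Keep the sentences; deleting them would leave only the windows, which do not secure the dosing minimum. An in-window date exists after every in-window previous visit: Visit 4 on Day 7, 8 or 9 allows Visit 5 on Days 14–16, 15–16 or 16, and Visit 5 on Day 14, 15 or 16 allows Visit 6 on Days 21–23, 22–23 or 23.

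The change is three numbers and the words for a minimum, issued by clarification letter or site memo. It adds no visits, patients or analyses, and the SAP is unaffected. The real cost is slack: permitted combinations fall from 27 to 10, and Visit 4 on Day 9 leaves only Day 16 and then Day 23. Sites should be told this, since Protocol 6.3 has missed visits rescheduled within 1–2 days.

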7.1.5 Visit 5 (Day 14 + 2 days)

Visit 5 needs should be scheduled 6 days after Visit 4 in order to ensure at least 7 days of q.d. dosing in the PM. The following procedures will be performed at Visit 5 (Day 14). Ophthalmic procedures should be performed in the order suggested below:

- BCVA
- Biomicroscopy
- Diurnal IOP
 - Measured using Goldmann applanation tonometer and a two-person reading method.
 - Readings at:
 - 8:00AM (± 30 mins)
 - 10:00AM (± 30 mins)
 - 4:00PM (± 30 mins)
 - Measure twice in each eye; if results differ by >1 mm Hg, a third measurement will be obtained. The mean will be taken if two measurements are used, for 3 measurements record the median.
- Collect used study drug and dispense a new bottle.
- Instruct subject to instill the last daily evening dose in the evening after the visit (suggested timing between 7:00PM and 9:00PM).

- Instruct subject to start dosing twice daily the day after the visit in the morning (suggested timing between 7:00AM and 9:00AM for the morning dose and between 7:00PM and 9:00PM for the evening dose).
- Blood pressure & heart rate
- Update concomitant medications, as needed
- Adverse event assessment

7.1.6 End of Study (Visit 6, Day 21 + 2 days)

Visit 6 needs should be scheduled 6 days after Visit 5 in order to ensure at least 6 days of b.i.d. dosing.

The following procedures will be performed at the End of Study visit (Visit 6) on Day 21. Ophthalmic procedures should be performed in the order suggested below:

- BCVA
- Biomicroscopy
- Diurnal IOP
 - Measured using Goldmann applanation tonometer and a two-person reading method.
 - Readings at:
 - 8:00AM (± 30 mins)
 - 10:00AM (± 30 mins)
 - 4:00PM (± 30 mins)
 - Measure twice in each eye; if results differ by >1 mm Hg, a third measurement will be obtained. The mean will be taken if two measurements are used, for 3 measurements record the median.
- Administer last dose of b.i.d. study drug in clinic after 8:00AM IOP is taken.
- Pachymetry
- Dilated ophthalmoscopy
 - After last IOP measurement is taken.
- Blood pressure & heart rate
- Blood chemistry, hematology
- UPT for women of childbearing potential
 - An adult woman is considered to be of childbearing potential unless she is one year post-menopausal or three months post-surgical sterilization.
- Collect used study drug.
- Update concomitant medications, as needed
- Adverse event assessment

- If a non-serious AE is unresolved at the time of the subject's final study visit, an effort will be made to follow up until the AE is resolved or stabilized, the subject is lost to follow-up, or there is some other resolution of the event.
- The Investigator should make every attempt to follow all SAEs to resolution.

7.1.7 Unscheduled Visits

Any visits or procedures performed beyond those specified within the protocol must be documented in the Unscheduled Visit pages of the eCRF. Subjects IOP should be checked at all unscheduled visits. Unscheduled visits may include but are not limited to reporting AEs, changes in concomitant medications, or ophthalmic assessments as deemed appropriate by an appropriately qualified physician.

7.1.8 Early Termination

In the event that a subject exits or is terminated from the study prior to the End of Study visit (Visit 6), every attempt will be made to ensure that the subject completes all Visit 6 assessments. If a non-serious AE is unresolved at the time of the subject's final study visit, an effort will be made to follow up until the AE is resolved or stabilized, the subject is lost to follow-up, or there is some other resolution of the event. The Investigator should make every attempt to follow all SAEs to resolution.

8 Study Assessments

The Schedule of Procedures and Assessments ([Appendix 1](#)) provides a list of study assessments and evaluations to be performed and the timing of each.

8.1 Efficacy Evaluations

Efficacy assessments will be conducted at the time points indicated on the Schedule of Procedures and Assessments ([Appendix 1](#)) and as detailed in the sections below.

8.1.1 IOP

IOP will be measured per the instructions in [Appendix 5](#).

8.2 Safety Evaluations

Safety assessments will be performed at the time points indicated on the Schedule of Procedures and Assessments ([Appendix 1](#)) and as detailed in the sections below.

- AE monitoring
- BCVA ([Appendix 3](#))
- Slit-Lamp Biomicroscopy ([Appendix 4](#))
- Central corneal thickness ([Appendix 7](#))
- Dilated ophthalmoscopy ([Appendix 6](#))
- Vital signs (heart rate and blood pressure) ([Appendix 12](#))
- Clinical laboratory tests (blood chemistry, hematology) ([Appendix 11](#))

8.2.1 Adverse Events (AEs) and Serious Adverse Events (SAEs)

AEs will be monitored throughout the study. Subjects will be encouraged to report any adverse findings during the study whether or not they are related to IP. These can be collected either in an unsolicited fashion without any prompting or in response to a general question such as: “Have you noticed anything different since you started the study; began the IP, etc?”

All AEs will be captured on the appropriate eCRF. Information to be collected at minimum includes event description, onset, assessment of severity, relationship to IP, and outcome.

The Investigator will record all AEs with start dates occurring any time after informed consent is obtained until 7 (for nonserious AEs) or 30 days (for SAEs) after the last day of study participation. At each study visit, the Investigator will inquire about the occurrence of AE/SAEs since the last visit. Events will be followed for outcome information until resolution or stabilization.

Any medical condition that is present at the time that the subject is screened will be considered as baseline and not reported as an AE. However, if the study subject's condition deteriorates at any time during the study, it will be recorded as an AE.

8.2.1.1 Definitions

An AE is any untoward medical occurrence in a patient or clinical study subject, temporally associated with the use of study intervention, whether or not considered related to the study intervention. An AE can therefore be any unfavorable and unintended sign (including an abnormal laboratory finding), symptom, or disease (new or exacerbated) temporally associated with the use of study intervention.

An AE or suspected adverse reaction is considered "serious" if, in the view of either the Investigator or Sponsor, it results in any of the following outcomes:

- Death,
- A life-threatening AE,
- Inpatient hospitalization or prolongation of existing hospitalization,
- A persistent or significant incapacity or substantial disruption of the ability to conduct normal life functions, or
- A congenital anomaly or birth defect.

Important medical events that may not result in death, be life-threatening, or require hospitalization may be considered serious when, based upon appropriate medical judgment, they may jeopardize the subject and may require medical or surgical intervention to prevent one of the outcomes listed in this definition.

